#### i. Follow up and Expected Outcomes

During the hospital stay, patients will be followed up for new laboratory results, changes in treatment plan and outcomes. The patient outcomes will be recorded as:

- a. time to defervescence;
- b. de-escalation or readjustment in antimicrobials;
- c. complete recovery and discharge vs. partial recovery and discharge vs. death.

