## Preliminary work done at Patan Hospital

Patan Hospital is a tertiary care medical center with 450 beds that admits between 10 to 30 febrile patients per week depending on the season. Over 30% of these patients do not have localizing signs and symptoms for clinical diagnosis nor do they have a laboratory-based diagnosis. These cases are labelled as undifferentiated fever and receive empirical treatment with two or more antimicrobial agents. Previous studies done at Patan Hospital have demonstrated that *Salmonella typhi* and *Salmonella paratyphi A* were causes of undifferentiated fever of >3 days duration in 34% patients and *Rickettsia typhi* in 17% cases, whereas another study in 2008 found 7% cases of febrile illness has *Rickettsia typhi*, which is the cause of Murine typhus [5,6]. These studies show an increase in cases of rickettsial infections including *Riackettsia typhi* and *Orientia tsutsugamushi*. Studies at Patan Hospital have also identified *Streptococcus pneumoniae*, *Leptospira* spp., *Orientia tsutsugamushi*, Hantavirus, and *Coxiella burnetii* as casues of febrile illnesses [4-6].

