## **B.** Specific Aims

Primary:

- 1. To estimate the proportion of additional infectious etiologies of febrile illness among patients presenting with an undifferentiated fever of 3 to 21 days duration.
- 2. To compare the use of antimicrobials in patients with undifferentiated fever in whom additional microbiological tests have been performed versus patients with clinical diagnosis alone.

Secondary:

- 3. To evaluate the appropriateness of the empiric antibiotic therapy based on clinical diagnosis alone and after laboratory confirmation.
- 4. To estimate the correlation between clinical diagnosis with laboratory diagnosis in patients with undifferentiated fever.
- 5. To compare the outcome among patients whose treatment is based on microbiological diagnosis compared to the patients whose treatment is based on clinical diagnosis alone.

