## Additional Evaluations for the Study

For patients without an obvious cause of fever and an inconclusive work up after standard of care evaluations, additional serological tests as a part of undifferentiated febrile illness work up will be performed, including:

- a. Clinical evaluation: includes thorough history and physical examinations based on a standard questionnaire and data collection tool
- b. Additional Microbiological Evaluations: If above listed laboratory and microbiological tests do not indicate a conclusive diagnosis, the patient's blood will be processed for additional Serological tests as a part of undifferentiated febrile illness work up. These tests will help to establish diagnosis of the following infections:
  - Murine typhus
  - Bartonellosis
  - Q-fever
  - Chikungunya
  - 7ika
  - Japanese B encephalitis
  - West Nile virus
- 5. Use of antimicrobials in the patients with and without an etiological diagnosis and their outcome at the time of discharge from the hospital will be recorded.
- g. Laboratory Methods

For the purpose of the study, following samples will be collected from 50% of randomly assigned patients for additional microbiological testing.

- 1. Blood cultures, 2 sets from 2 different sites from all study patients (20 mL total)
- 2. Serum samples for serological testing (4 mL)

After obtaining appropriate consent, total 25 mL blood will be collected from each patient assigned to the additional testing arm. Blood samples will be cultured in liquid media and held in the incubator for 7-days.

Urine will be taken to the lab for routine examination and culture will be performed only if there are >10 pus cells or patient reports urinary symptoms.

Gram stain, AFB stain and Genexpert will be performed on sputum samples.

As a part of routine febrile illness work up, the serum samples will be tested for HIV, scrub typhus, dengue, leptospirosis, brucella, malaria, and kala azar.

Additional serum sample will be processed for further serological testing for Chikungunya, Zika, *Coxiella burnetii* (Q-fever), *Bartonella henselae* (Bartonellosis), *Rickettsia typhi* (murine typhus), Japanese B encephalitis, and West Nile virus using ELISA and/or Rapid Diagnostic Test (RDT), as applicable. Although molecular tests have a higher sensitivity and specificity, molecular testing has not been planned for this study because of the budget limits.

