For Specific aims 2 and 3, total daily defined dose (DDD) for each antimicrobial agent received by patients will be calculated following WHO guidelines. The total DDD, number of antibiotics, and Duration of antibiotics used will be compared between the groups by calculating Means/SD/95% confidence intervals. Similarly, appropriateness of antibiotic uses will be tested with cross-tabulation using Chi-square analysis.

For specific aim 4, pre-test probability and post-test probability will be determined by both using standard calculations and using Fagan's Nomogram. Correlations between pre- and post-test probabilities for bacterial, rickettsial, viral vs. other causes will be evaluated.

For specific aim 5, the hazard ratio using the Cox proportional hazard model will be calculated to compare the outcomes between the groups. Since multiple factors, such as comorbidities, severity of illness at baseline, type of infection and host immune status, can influence the outcomes, adjustment for these factors will be considered during the univariate and multivariate outcome analyses. Updated Charlson comorbidity index (Quant et al.) will be calculated and used for comparison between the groups [15]. Similarly, qSOFA will be used to stratify the patients by severity of infection [16].

REDCap (Research Electronic Data Capture) software will be used for questionnaire and database entry. SPSS version 25 (IBM, USA) will be used for statistical analysis.

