## **10. STUDY TIMELINE**

Events	Details	Timeline
	IRC approval	Jan 2025
Preparatory Phase	Team preparation	Oct-Dec 2024
	Lab setup/supplies	Oct-Dec 2024
	Enrollment (12 months)	1 Feb 2025- 31 Jan 2026
Interventional Phase	Laboratory tests	1 Feb 2025- 31 Jan 2026
interventional Filase	Follow up	1 Feb 2025- 31 Jan 2026
	Data Collection	1 Feb 2025- 31 Jan 2026
Data Analysis and	Statistical analysis	1 Feb 2026- 31 Mar 2026
Reporting Phase	Report and Manuscript preparations	Apr-Jun 2026

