# E. Antimicrobials Dose and Durations

	Antimicrobial agent used	Route	Total Dose per day (Grams)	Total No. of days used
AM1		PO, IV	grams	No. of days
AM2				
AM3				
AM4				
AM5				
AM6	Appropriateness of Antimicrobials used (to be determined by an independent physician)	Yes, No, Partially		

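### The counting window for antimicrobial use (primary aim 2) is not fixed, and the form has no dates to separate use before randomisation, in hospital and after discharge

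*Protocol*

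**What the plan says.** Specific aim 2 (protocol section 4.B, listed as primary) is "To compare the use of antimicrobials in patients with undifferentiated fever in whom additional microbiological tests have been performed versus patients with clinical diagnosis alone". Section 5.j names the measures: "The total DDD, number of antibiotics, and Duration of antibiotics used will be compared between the groups by calculating Means/SD/95% confidence intervals". No start or end point is attached to them.

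The places that bear on the window are:

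- **Follow-up, section 5.i:** "During the hospital stay, patients will be followed up for new laboratory results, changes in treatment plan and outcomes". No contact after discharge is described anywhere.
- **Additional Evaluations, item 5:** antimicrobial use is recorded, and "their outcome at the time of discharge from the hospital will be recorded". The reference to discharge may belong to the outcome alone.
- **Appendix 1, section E:** for each agent, the route, the daily dose in grams and "Total No. of days used". There are no dates and no mark for inpatient or discharge treatment.
- **Appendix 1, Randomization Result:** an admission date, but no randomisation date.
- **Timing of randomisation:** section 5.c requires that routine tests, including cultures, give no obvious diagnosis. Appendix 1 places randomisation after eligibility and consent.
- **Section 2, preliminary work:** patients labelled with undifferentiated fever "receive empirical treatment with two or more antimicrobial agents".

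**The concern.** A total of drug use can be interpreted only when its window is known and is the same in both arms. Here the two ends raise different problems.

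**End of the window.** If counting stops when the patient leaves, it stops at an event after randomisation. In an open-label trial whose purpose is to change management, a test result may change when a patient goes home or whether a course is finished there. The in-hospital total could then fall with no antimicrobial saved, or a real saving made after discharge could go unseen.

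**Start of the window.** Patients enter after an inconclusive work-up, so some will plausibly have been treated already. The added tests cannot change that use. If it is summed into the endpoint, it adds variation common to both arms and makes relative effects smaller. It also prevents an already treated patient from ever counting as a non-user.

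The gap lies in what is collected. An analysis plan could define a window, but could not apply it to a form without dates unless someone went back to the charts.

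**Working it through.** **1. The plan's own figure.** Section 5.j sizes the antimicrobial comparison on use falling from 90% to 75%, with 80% power. (It labels this aim 1, although antimicrobial use is aim 2 in section 4.B.) With two-sided alpha 0.05 (sidedness assumed) and unpooled variance:

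n = (1.960 + 0.842)² × (0.90×0.10 + 0.75×0.25) / 0.15² = 7.849 × 0.2775 / 0.0225 = 96.8, so 97 per arm.

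The stated 97 is reproduced. The pooled-variance formula gives 100, so its power at 97 is 79%.

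**2. What the form can separate.** Section E gives total days per agent. Splitting these at randomisation needs a randomisation date and drug start dates. Splitting them at discharge needs a discharge date and stop dates, or a discharge-prescription field. None of these is in the questionnaire.

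**3. End of the window (illustration).** The protocol gives no lengths of stay, so these are assumed. Recorded days = min(course, stay).

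- Same 10-day course, discharge on day 6 v day 5: 6 v 5 recorded days, 1/6 = 17% apparent reduction, true difference zero.
- Same course, day 7 v day 6: 1/7 = 14%. Day 7 v day 5: 2/7 = 29%.
- The reverse: courses of 10 v 8 days, both discharged on day 6, give 6 v 6 recorded days. A true 20% reduction disappears.

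**4. Start of the window, totals (illustration).** Take 8 recorded days, 3 of them before randomisation, and a true cut of 2 days. The cut is 2/5 = 40% of the days that could change, but 2/8 = 25% of the recorded total. The difference is 2 days either way, so the contrast in days is diluted only in relative terms.

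The variance does rise. Let r be the SD of pre-randomisation days divided by the SD of later days, the two being independent. Suppose later days alone give 80% power at 97 per arm, a standardised effect of 2.802 × √(2/97) = 0.40. Then power = Φ(2.802/√(1+r²) − 1.960):

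| r | 0 | 0.25 | 0.5 | 0.75 | 1 |
|---|---|---|---|---|---|
| power | 80% | 78% | 71% | 61% | 51% |

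**5. Start of the window, any use v none.** Let a share f be treated before randomisation and counted as users in both arms, independently of later use. The rates become f + (1−f)×0.90 and f + (1−f)×0.75, and the difference is (1−f) × 15 points. At 97 per arm (pooled formula):

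| f | rates | difference | power | n per arm for 80% |
|---|---|---|---|---|
| 0 | 90% v 75% | 15 points | 79% | 100 |
| 0.25 | 92.5% v 81.25% | 11.25 points | 64% | 141 |
| 0.5 | 95% v 87.5% | 7.5 points | 46% | 222 |
| 0.75 | 97.5% v 93.75% | 3.75 points | 25% | 466 |

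The independence assumption matters. If the already treated patients all lie among those who would be users in either arm, nothing is lost until f passes 75%. Beyond that the test arm cannot fall below f: power is 50% at f = 0.80 and 18% at f = 0.85.

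**The case against.** **The window is inferred.** No sentence says that discharge courses are left out or that earlier days are counted. Section 5.h records all available treatment, and the days field in section E has no inpatient limit, so staff could enter a planned discharge course. This stands: what can be shown is an undefined window, not a wrong one. It does not remove the problem, because staff may then fill in the field differently from patient to patient.

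**Pre-randomisation use does not bias the comparison.** A reader might infer that it distorts the arm contrast. It does not, because randomisation makes it equal by arm in expectation. The harm is lost precision and interpretability.

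**Section 2 gives no timing.** It reports empirical treatment of these patients but not whether it starts before enrolment. This also stands: prior exposure is plausible from the order of work-up and randomisation, but its extent is unknown. The measures listed for aim 2 are also totals and counts; any use v none is the scale of the sample-size calculation.

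**The calendar does not add to the case.** A reader might infer from section 10, which gives both enrolment and follow-up as "1 Feb 2025- 31 Jan 2026", that the last patients are cut short. But 234 patients at 20 per month take 11.7 months, about 356 days, which leaves about 9 days. A 7-day stay then loses nobody, and a 14-day stay about (14 − 9.1) × 240/365 = 3 patients. The table is a planning timeline, not a rule to stop following inpatients.

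**In-hospital use is a legitimate endpoint.** It is, if it is named as such. It answers a narrower question than aim 2 poses.

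**Conclusion.** The point holds as a gap in definition and data capture for a primary aim. The protocol does not fix the window for antimicrobial use, and the form cannot separate use before randomisation, in hospital and after discharge.

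On the natural reading the totals end at discharge, and the arm contrast can then partly measure length of stay or a move to home treatment. That bias needs two conditions: discharge courses left uncounted, and discharge timing or home treatment that differs by arm. The protocol states neither, so the direction is unknown and the 14% to 29% in the examples is illustrative only.

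Pre-randomisation use costs power and dilutes relative effects. The loss runs from nothing to severe, depending on how many patients are already treated and on how that relates to later use.

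This should be fixed. It does not by itself invalidate the trial.

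**What to change.** 1. Add to Appendix 1 the randomisation date, the discharge date, a start and stop date for each agent, and the discharge prescription (agent, dose, route, days prescribed).
2. State in section 5.j that the arms are compared on DDD, number of agents and duration from randomisation to the end of the prescribed course, with in-hospital use as a supporting result.
3. Use exposure before randomisation as a baseline covariate and leave it out of the endpoint.

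The cost is a few fields copied from the chart and the discharge prescription, with no extra visit and no change to anyone's treatment. The downside is that days after discharge are prescribed rather than observed, which should be said when the result is reported.

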## j. Data Collection, Data Analysis and Sample Size

Demographic, clinical, radiological, and laboratory data will be collected and entered into a password protected database. To minimize the errors, data will be directly entered into the database using REDCap Database questionnaires.

Data analysis will include the followings:

- 1. Demographics and baseline characteristics of patients will be analyzed and compared between the two groups.
- 2. Clinical diagnosis and laboratory confirmation of diagnosis will be used to estimate the proportions of various infectious etiologies of febrile illness in patients presenting with a febrile illness of 3-21 days duration. (Specific aim-1)
- 3. Number, type, dose and duration of antimicrobials used to treat the patients will be collected and compared between the two groups: clinical diagnosis alone versus clinical plus microbiological diagnosis. (Specific aim 2)
- 4. Appropriateness of the empiric antibiotic therapy will be determined by an independent physician expert after the laboratory confirmation of the diagnosis. Comparison between the two groups (clinical diagnosis vs. microbiological diagnosis) will be done by calculating the proportion of cases who received appropriate antibiotics divided by the total number of cases for whom empiric antibiotics were administered. (Specific aim-3)

- 5. Pretest probability for clinical diagnosis and posttest probability after laboratory-based diagnosis will be calculated and correlated for bacterial, rickettsial, viral infections versus other causes of fever. (Specific aim-4)
- 6. Clinical outcomes will be compared for patients whose treatment is based on clinical diagnosis alone (Group 1) versus the patients whose treatment is based on clinical plus microbiological diagnosis (Group 2). Composite Positive outcome (complete or partial recovery) and Negative outcome (in-hospital death) will be compared between the two groups. (Specific aim-5)

Demographics and baseline characteristics of patients will be expressed in percentages, means±SD, 95% confidence intervals, and/or median±IQR, as appropriate. Proportions will be compared between the two groups with Chi-square tests. Numerical variables will be expressed as Means/SD/95% confidence intervals and Median/IQRs, whereas Student T test or Mann-Whitney test, respectively, will be used for statistical comparisons. Alpha will be set at 95% (level of significance, p <0.05).

For Specific aims 2 and 3, total daily defined dose (DDD) for each antimicrobial agent received by patients will be calculated following WHO guidelines. The total DDD, number of antibiotics, and Duration of antibiotics used will be compared between the groups by calculating Means/SD/95% confidence intervals. Similarly, appropriateness of antibiotic uses will be tested with cross-tabulation using Chi-square analysis.

For specific aim 4, pre-test probability and post-test probability will be determined by both using standard calculations and using Fagan's Nomogram. Correlations between pre- and post-test probabilities for bacterial, rickettsial, viral vs. other causes will be evaluated.

For specific aim 5, the hazard ratio using the Cox proportional hazard model will be calculated to compare the outcomes between the groups. Since multiple factors, such as comorbidities, severity of illness at baseline, type of infection and host immune status, can influence the outcomes, adjustment for these factors will be considered during the univariate and multivariate outcome analyses. Updated Charlson comorbidity index (Quant et al.) will be calculated and used for comparison between the groups [15]. Similarly, qSOFA will be used to stratify the patients by severity of infection [16].

REDCap (Research Electronic Data Capture) software will be used for questionnaire and database entry. SPSS version 25 (IBM, USA) will be used for statistical analysis.

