## Sample Size:

For this study, a total of 234 randomly selected patients with acute undifferentiated febrile illness will be enrolled with a fever of 3 days duration. Of these 234 patients, 117 will be randomly assigned to undergo additional microbiological testing.

Based on previous studies and number of patients needed to include less common seasonal infections, this study will enroll patients throughout a period of 12 months. Cluster sample technique will be used to select 20 patients per month including 10 patients who will be randomly selected to undergo additional microbiological testing.

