#### Sample size determination and assumptions:

For specific aim 1, a reduction of antimicrobial use in about 15% patients is expected after additional laboratory confirmation of the diagnosis including viral infections. Assuming this decrease in antibiotics from 90% to 75%, 95% confidence interval, and 80% power, required sample size would be 97 in each arm. With similar assumptions for specific aim 3, an improvement in antimicrobial therapy from 70% to 90% would require 59 patients.

For specific aim 2, assuming an improvement in identification of causative agents from 30% to 50%, 95% confidence interval, and 80% power, required sample size would be 91.

For specific aim 5, an improvement in clinical outcome for patients whose treatment is based on microbiological diagnosis by 20%, from 60% to 80%, 95% confidence interval, and 80% power, the required sample size would be 79 in each arm.

Based on above calculations, minimum sample size needed would be 97 in each arm. Including a 20% loss for failure to consent and loss to follow up, total sample size needed will be 117 in each arm.

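### Primary aim 2 compares antimicrobial use on at least three measures under one general p<0.05, with none named as deciding, and the measure the trial is sized on is not among them

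*Protocol*

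**What the plan says.** Under Specific Aims, the second primary aim reads "To compare the use of antimicrobials in patients with undifferentiated fever in whom additional microbiological tests have been performed", set against patients with a clinical diagnosis alone. It names a topic and no variable.

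Section 5.j, item 3, tagged to aim 2, states: "Number, type, dose and duration of antimicrobials used to treat the patients will be collected and compared between the two groups". Later in 5.j, for aims 2 and 3 together, the list differs: "The total DDD, number of antibiotics, and Duration of antibiotics used will be compared between the groups by calculating Means/SD/95% confidence intervals". For numerical variables in general, "Student T test or Mann-Whitney test, respectively, will be used for statistical comparisons". The level is given once for everything: "Alpha will be set at 95% (level of significance, p <0.05". The 95% there is evidently the confidence level, so I read the significance level as 5%.

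The sample size section uses another quantity, under the label of specific aim 1: "Assuming this decrease in antibiotics from 90% to 75%, 95% confidence interval, and 80% power, required sample size would be 97 in each arm". This is a proportion of patients, and neither 5.j list contains it.

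**The concern.** When a primary question is answered on several measures, each at 5%, and nothing says which one decides, the chance of a positive answer by luck alone exceeds 5%. The plan also does not say how to read a split result. Fewer agents but a longer duration could be reported as success or as failure.

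The usual fallback is to take the sized quantity as the intended primary measure. That does not work here, because the sized proportion is not in the aim 2 analysis and carries another aim's label. At stake are the meaning of the 5% level for primary aim 2 and the link between the power statement and the analysis.

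**Working it through.** **Inputs from the protocol.** There are three measures in the operational list for aims 2 and 3 (total DDD, number, duration), and item 3 adds type and dose. The level is 0.05. The sizing assumption is 90% versus 75% with 80% power, giving 97 per arm, raised to 117 per arm.

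**Assumptions.** Tests are two-sided, which the protocol does not state. The correlation between the test statistics is also not given, so a range is shown.

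**Step 1: reproduce the plan's figure.** For two proportions with unpooled variance, n = (1.96 + 0.842)² × [0.90×0.10 + 0.75×0.25] / 0.15² = 7.85 × 0.2775 / 0.0225 ≈ 96.8, so 97 per arm. This matches the stated figure and supports the two-sided reading. The one-sided pooled version gives 79, or 92 with continuity correction. The plan's inflation is 97 × 1.2 = 116.4, so 117.

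The power statement therefore belongs to a comparison of two proportions. It says nothing about power for total DDD, number of agents or duration.

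**Step 2: three measures, independent tests.** The chance of at least one p<0.05 with no true effect is 1 − 0.95³ = 14.3%. Counting only false claims of reduced use (0.025 per test), it is 1 − 0.975³ = 7.3%.

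**Step 3: three measures, correlated tests.** This is a simulation of equally correlated normal test statistics, with 1,000,000 draws and two-sided 0.05.

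| Assumed correlation | Any false claim | False claim of reduced use |
|---|---|---|
| 0 | 14.3% | 7.3% |
| 0.5 | 12.5% | 6.3% |
| 0.7 | 10.9% | 5.5% |
| 0.8 | 9.8% | 4.9% |
| 0.9 | 8.4% | 4.2% |
| One measure only | 5.0% | 2.5% |

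**Step 4: if more measures are tested.** With four (type added, and dose and DDD counted as one), any false claim runs from 9.4% at correlation 0.9 to 18.5% if independent. With five (dose and DDD counted separately), it runs from 10.1% to 22.6%.

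**Step 5: what dividing the level would cost.** Suppose the 90% versus 75% comparison were one of three tested at 0.05/3 = 0.0167. By the pooled formula it would need 133 per arm, against 100 at 0.05. Power would be about 64% at 97 per arm and 74% at 117, against 79% and 86% at the full 0.05.

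**The case against.** **The count.** A reader might infer five separate tests and an error rate of 10 to 23%. The text does not support that as the headline. Total DDD is calculated from the recorded dose and days of use, so dose and DDD are most naturally one measure. Type has no defined variable or categories, and the later list does not carry it forward. The 22.6% figure also needs five independent tests, which is not credible when DDD is built from dose and duration. This objection stands, and three measures is the fair base case.

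**Direction.** The hypothesis is that use will fall, so the error that matters most is a false claim of reduction. That rate is about half the two-directional one. This also stands, and both rates are given.

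**Estimation or testing.** The later list speaks of means and confidence intervals, which could be read as estimation only. This weakens the point without removing it. The general rule in the same section prescribes tests for numerical variables at p<0.05, and checking whether a 95% interval for the difference excludes zero is the same 5% test.

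**Left to the SAP.** The order of testing and the adjustment are often left to a SAP, which may exist. The fault lies in what the protocol itself states: two lists that do not match, one unadjusted level, and a sample size for a quantity in neither list. A SAP could not name the deciding measure without departing from some part of this text.

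**Pilot status.** The limitations section calls this a pilot for larger studies, which moderates the consequences. But the protocol also states a directional hypothesis, 80% power and an expectation that the results will be useful for treating patients.

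**Conclusion.** The point holds. Primary aim 2 has no deciding measure, at least three measures share one general 5% level, and the quantity that sets the sample size is outside the analysis. For the three measures, the chance of at least one false positive is about 8 to 14%, and of a false claim of reduced use about 4 to 7% against 2.5%. These figures assume two-sided tests and equal correlations from 0.9 to 0. Because the measures are related, the independent-test figures are upper bounds for three tests. The rates rise if type and dose are tested in their own right. The interim analyses are a separate matter and are not counted here.

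**What to change.** In section 5.j, name one deciding measure for aim 2, tested at two-sided 0.05, and make it agree with the sample size section in one of two ways:

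- Make the sized proportion (90% versus 75%) the deciding measure, define what counts as use, and add it to the aim 2 analysis.
- Choose another measure, such as total DDD, number of agents or duration, and restate the assumptions and power for it.

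In either case, correct the aim label in the sample size section, which attaches antimicrobial use to aim 1.

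Test the remaining measures in a written fixed order after the deciding one. Alternatively, once the deciding measure is significant, apply Holm among them (for three: 0.0167, 0.025, 0.05), or report them as supportive. Give type and agent-level DDD with confidence intervals only.

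The cost is a paragraph in 5.j and a matching edit to the sample size text. The first option keeps the full 0.05 and the stated sample size basis. The second may change the required number, which cannot be worked out from this document because it gives no standard deviations. The non-deciding measures face a harder threshold or carry no claim.

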#### **Randomization Result**

	Information	Remarks
Patient's study ID no.	D001, D002, D003,	
Date of Birth (in AD)	DD/MM/YYYY	
Address (District where patient lives)	District name	
Admission date (in AD)	DD/MM/YYYY	
Unit location	Ward, HDU, ICU	
Randomization Arm	Group A, Group B	

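### The protocol randomises patients to additional testing, but its analysis section labels the compared groups by type of diagnosis or basis of treatment and never ties them to the randomised arms

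*Protocol*

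**What the plan says.** Several places define the comparison by assignment to testing:

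- Sample Size: "Of these 234 patients, 117 will be randomly assigned to undergo additional microbiological testing".
- Section 4.B, aim 2: patients "in whom additional microbiological tests have been performed versus patients with clinical diagnosis alone".
- Appendix 1, Randomization Result: the arm is recorded as "Group A, Group B". Section C of the questionnaire restricts the seven extra serologies to Group B.
- Sample size determination: the antimicrobial-use calculation (90% to 75%) and the aim 5 calculation (60% to 80%) are both given per arm. The antimicrobial-use calculation is printed under aim 1, although antimicrobial use is aim 2 in section 4.B.

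Other places describe the groups by something known only after randomisation:

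- Section 5.j, item 3 (aim 2): antimicrobial use is compared for two groups described as "clinical diagnosis alone versus clinical plus microbiological diagnosis".
- Section 5.j, item 4 (aim 3): the two groups are again labelled by clinical or microbiological diagnosis.
- Section 5.j, item 6 (aim 5): "patients whose treatment is based on clinical diagnosis alone (Group 1") against "the patients whose treatment is based on clinical plus microbiological diagnosis (Group 2"). Aim 5 in section 4.B has the same construction.
- Section 5.f, Additional Evaluations, item 5: "Use of antimicrobials in the patients with and without an etiological diagnosis" is to be recorded.

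The later paragraphs of section 5.j on aims 2, 3 and 5 refer only to the groups, without saying which.

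**The concern.** Every enrolled patient has no obvious diagnosis after the routine work-up. A Group B patient whose additional tests are all negative therefore still has only a clinical diagnosis, and by the wording of section 5.j belongs with the comparison group. Item 6 goes further, because what treatment rests on depends on what clinicians do after randomisation.

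If an analyst followed that wording, membership of the microbiological group would be decided partly by the disease the patient has. Patients with a detectable infection can differ in cause, severity and need for antimicrobials from those without one. The contrasts for aims 2, 3 and 5 would mix that difference with the effect of testing, and the protection that randomisation gives would be lost. Power would also change, because the groups would no longer be 117 and 117.

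**Working it through.** **1. The planned size is for full arms.** Inputs from the sample size section: 90% v 75%, 80% power, 5% significance (two-sided assumed).

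n = (1.96 + 0.8416)² × [0.90×0.10 + 0.75×0.25] / 0.15² = 96.8, so 97 per arm. With the 20% allowance, 97 × 1.2 = 116.4, so 117. Both stated figures reproduce.

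**2. How many patients the literal reading would move.** The protocol targets identification in 50%. It does not say whether this applies to enrolled patients, who have no diagnosis on routine work-up, so 30% is shown as a lower case.

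- 50% yield: 117 × 0.50 = 58.5 tested patients without an etiology.
- 30% yield: 117 × 0.70 = 81.9.

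**3. Bias when testing has no effect (hypothetical).** Assume 90% use in both arms, 30% of Group B detected (35.1 patients), and use u in detected patients. The protocol gives no value for u. All of Group A stays in the comparison group; late routine results in Group A are not modelled. The other 234 − 35.1 = 198.9 patients have use (234×0.90 − 35.1u)/198.9, so the apparent difference is

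(234/198.9) × (0.90 − u) = 1.176 × (0.90 − u).

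| u in detected patients | Apparent difference (others minus detected) |
|---|---|
| 75% | +17.6 points |
| 85% | +5.9 points |
| 90% | 0 |
| 95% | −5.9 points |

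Compared by randomised arm, the expected difference is 0 in every row.

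**4. Power if the contrast is 90% v 75%.** Power = Φ[(0.15 − 1.96·se₀)/se₁], with se₀ from the pooled proportion and se₁ from the separate proportions.

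For 117 v 117: se₀ = √(0.825×0.175×2/117) = 0.0497 and se₁ = √((0.09 + 0.1875)/117) = 0.0487. Then (0.15 − 0.0974)/0.0487 = 1.08, giving 86.0%.

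| Groups compared | 30% yield | 50% yield |
|---|---|---|
| Detected v Group A (117) | 60.7% | 72.6% |
| Detected v everyone else | 66.5% | 78.5% |
| Group A v Group B as randomised | 86.0% | 86.0% |

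The first two rows hold the difference at 15 points for whichever groups are formed. If the effect of testing were concentrated in detected patients, their contrast would be larger and the power loss smaller, but the contrast would still be confounded.

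**The case against.** The strongest reply is that section 5.j is using shorthand for the arms. In aim 2, clinical diagnosis alone plainly means not additionally tested, and item 3 reuses that phrase and is tagged to aim 2. The study is called randomised, two of the sample sizes are per arm, and item 1 compares baseline characteristics between the two groups, which fits the arms. Nothing says that test-negative Group B patients are moved or excluded. Section 5.f, item 5, says only what is recorded and sets no contrast. A separate analysis plan may define the analysis population.

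Much of this stands. A reader might infer that the protocol breaks the randomisation outright; the documents do not support that, because comparison by arm is a fair reading of aim 2. A reader might also infer that most tested patients will stay undiagnosed; the only stated target implies about half, and only a lower yield would make it most.

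The hypothetical is limited too. Use in detected patients is assumed, and it could be higher rather than lower, since murine typhus, bartonellosis and Q fever are bacterial. The calculation also concerns any use versus none, whereas section 5.j lists number, type, dose and duration, and total DDD.

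The reply does not remove the problem in item 6 and aim 5, where the groups are defined by the basis of treatment and given labels (1 and 2) that differ from the database labels (A and B). Nor is the point merely a missing intention-to-treat sentence: the protocol states a grouping that conflicts with its own randomisation. An analysis plan that followed it would inherit the conflict, and one that departed from it would contradict the protocol.

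**Conclusion.** The point holds as an internal contradiction about who is compared. It is clearest for secondary aim 5 and also affects primary aim 2 and secondary aim 3. On the literal reading, about half of Group B (more if the yield is below 50%) would be counted with the comparison group and the contrast would not be randomised.

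The direction and size of the resulting bias cannot be fixed from the protocol, because they depend on antimicrobial use in detected patients. Under the stated assumptions (no testing effect, 90% use overall, 30% of Group B detected), the false difference is 6–18 points at 75–85% use, nil at 90%, and reversed above that. For comparison, the planned effect is 15 points. Power for a 90% v 75% contrast would be about 61–79% instead of 86%, on the assumption that the 15-point difference is unchanged by the regrouping.

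**What to change.** In section 5.j, items 3, 4 and 6, and in the later paragraphs on aims 2, 3 and 5, state that Group A (standard work-up) is compared with Group B (standard work-up plus additional testing), with patients analysed as randomised whatever the test result. Replace the Group 1 and Group 2 labels with the database labels.

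Align the wording of aim 5 in section 4.B, of item 5 in section 5.f, and of the sample size assumptions. Keep any comparison by diagnosis obtained as descriptive or exploratory.

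The change is to wording only. It needs no additional patients or tests and matches the full arms that the sample size already assumes. The price is that the by-arm effect may be smaller than a contrast confined to test-positive patients, but it is the one that randomisation supports.
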